A change to, or non-compliance with, the IRB-approved procedures without prior Sponsor and IRB approval (excluding changes made to eliminate apparent immediate hazard to participants). A violation may affect health, safety, or rights of a participant. Any violation will be reported immediately to the Sponsor for guidance on reporting.

If the protocol deviation/protocol violation does not represent a significant alteration in the approved protocol and/or affect the safety or welfare of the participant, it will be reported to the UAMS IRB at the time of Continuing Review. If the protocol deviation/violation represents a significant alteration in the approved protocol and/or if it affects the safety or welfare of the participant, it must be reported to the Sponsor and UAMS IRB immediately.

Study Stopping/Pausing

This study is low risk, and no adverse experiences are anticipated. The device is being designed with adherence to all the safety considerations established in IEC 60645-5. Each device will be labeled with a unique identifier that will correlate with specific hardware and firmware versions to allow performance and any adverse events to be recorded and a full root cause analysis (RCA) to be performed. If there are concerns during measurement such as discomfort reported by the patient, or device malfunction reported by the clinician, testing will be stopped immediately. The issue will be documented, reported to the PI, and the device will no longer be used until a full RCA has been performed. If this issue can be resolved immediately, then testing will be restarted with the participant. If the issue cannot be resolved immediately (i.e., within the duration of the clinical appointment), then the data will be considered incomplete and additional participants will be recruited in order to meet recruitment goal of 40 adult ears with complete data and 20 child ears with complete data. The participant will still receive the \$20 gift card. While both ears will be tested, if data can only be obtained in one ear, the participant will still be considered to have completed the study as long as results from both the devices can be obtained for that ear. Any safety concerns will be reported to the PI, ORRA, and the UAMS IRB. Any event related to changes in consent form, protocol, or inadvertent disclosure of confidential information will be reported to the IRB.

Data Analysis

Pilot Validation Analysis

Analyses for the pilot validation will include: 1) comparison of categorical classifications of tympanogram types for the commercial vs prototype devices; 2) evaluating potential intra-participant correlation between ears; 3) assessing differences in numerical measures between the commercial and prototype tympanometer; and 4) evaluating performance of mHealth tympanometer and commercial tympanometer.

- 1) For each device, commercial and prototype, tympanograms will be categorized into one of 3 categories: A, B and C. To assess the agreement between the two devices with respect to categories, Bowker's test of symmetry and the Kappa coefficient conventional methods to assess agreement, will be used. For the initial analysis, both tympanograms will be performed for each ear and no adjustments will be made for participants (i.e., most will have both ears included).
- 2) To assess the potential effect of participant and ear status (normal, diseased) for participants where both ears are included, each participant's ears will be characterized as (both normal, both diseased, one diseased and one normal). Within those categories, the number of ears for which there is concordance between the two tympanograms for each participant will be 0, 1 or 2. Pearson's chi-square test will be used to compare the three groups defined by ear status with respect to the distributions of the number of ears with concordance.
- 3) The Wilcoxon signed rank test will be used to determine if the differences in the numerical measures (ear canal volume, static admittance and tympanometric peak pressure) obtained from the commercial and prototype devices are significantly different from zero. No adjustment for multiple testing is planned.
- 4) Audiologist assessment of the mHealth and commercial tympanometers will be captured through questionnaires which assess 4 performance measures using a 5-point Likert scale. For each performance measure, the Kappa coefficient and Bowker's test of symmetry will be used to assess agreement between the two mHealth and commercial tympanometers with respect to responses.

A minimum of 30 participants will be enrolled. Both ears will be used for each patient enrolled, with enrollment remaining open until 60 ears (40 adult and 20 pediatric ears) are accrued to ensure that there are sufficient number of ears for analysis. It is possible that more than 30 participants will be required to accrue 60 ears if we are unable to obtain a tracing on one or both ears in certain patients (such as due to a draining ear, which inhibits formation of a seal). We anticipate consenting no more than 40 individuals to reach the enrollment goal of 30 participants. With a sample size of 30 participants (60 ears), a null hypothesis where kappa is 0 (no correlation between devices) can be tested against the alternative hypothesis of kappa of 0.3 using a two-sided 0.05 significance level with a power of 0.89.

Title: "Pilot Validation of a Prototype Mobile Health Tympanometer"
PI: [name], MPH
Institution: University of Arkansas for Medical Sciences

Machine Learning Algorithm Analysis

The categorizations of the tympanogram (Type A, B, C) classified by the algorithm will be compared with the audiologists' interpretations. To assess agreement between the audiologist and the algorithm, Kappa analysis and Bowker's test of symmetry will be performed.

Ethical Considerations

This study will be conducted in accordance with all applicable government regulations and UAMS research policies and procedures. This protocol and any amendments will be submitted and approved by the IRB as required.

For recruitment and eligibility determination, a partial HIPAA waiver will be obtained. PHI access under the partial HIPAA waiver will entail using the clinic schedule to screen for potential participants by their age and reason for visit. Reason for visit will be used to determine middle ear status and whether tympanometry is likely to be performed as part of the clinical visit.

For eligible participants and parents/guardian of eligible children, informed consent using IRB-approved consent materials, will be obtained before the participant begins any study procedures and will be performed electronically using a secure REDCap database. All participants for this study will be provided an electronic informed consent form (e-consent) describing this study in language understandable to the study population.

Consent materials will provide sufficient information for participants/parent/guardian to make an informed decision about participation in this study. The person obtaining consent will thoroughly explain what the participants/parent/guardian need to know about the study, including study requirements, and study risks and benefits.

The consent process will take place while the prospective participant is attending their audiology evaluation in the audiology clinic. The consent discussion will occur prior to routine tympanometry. Participation privacy will be maintained, and questions regarding participation will be answered. No coercion or undue influence will be used in the consent process.

This consent form must be signed by the participant or parent/guardian and the person obtaining the consent. An e-consent form will be presented to the participants/parent/guardian for review, which may be electronically signed. The participant/parent/guardian will receive an electronic copy of the signed consent form execution, and if requested, a hard copy will be provided. The informed consent process will be documented in the electronic medical record. We will obtain informed consent for adults 18 years and older. In case of eligible children, informed consent will be obtained from parent/guardian and an assent will be sought from children 7 years and above in accordance with **UAMS IRB Policy 17.1 Special Populations: Children in Research** and parental consent will be obtained.

Title: "Pilot Validation of a Prototype Mobile Health Tympanometer"
PI: [name], MPH
Institution: University of Arkansas for Medical Sciences

Compensation

Adult participants and families of child participants will receive a \$20 electronic gift (e-gift) card after completing the study. Participants will complete a gift card form in REDCap that will be separate from study data. The e-gift card will be provided through UAMS approved e-gift card system and sent to the participant's (or caregiver's) email address. If the participant prefers not disclosing their email address in REDCap, a research email account will be used to process the e-gift card and a printout of the e-gift card will be provided to the participant.

Data Storage and Sharing

Data from the study will be stored in electronic medical records, paper forms, a secure REDCap database and/or UAMS Box. Any deidentified data from the study necessary for refinement of the device will be shared with our biomedical engineer collaborators at Duke University. This pilot validation study will support a larger NIH-funded R33 grant application, with University of Pretoria, our commercial collaborator hearX, and Duke University as partners. Data from the validation study will be shared with our partners as needed to prepare the R33 grant application, which involves a larger clinical validation study. Duke University, University of Pretoria, and hearX will have access to deidentified data that will be shared via a secure REDCap database. Deidentified raw data and aggregate findings of the study will be shared with these collaborators for the continued co-development of the mHealth tympanometer.

Dissemination of Data

Results of this study may be used for presentations, posters, or publications. The publications will not contain any identifiable information that could be linked to a participant. The study will be listed on ClinicalTrials.gov, and information will be updated in a timely manner in accordance with FDA and institutional requirements.

References

3. Organization WH: **Childhood hearing loss: act now, here's how.** 2016, :13-p.

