Eligible patients will be invited to participate, and the consent form reviewed. Consented participants will receive their audiological services as scheduled, with the addition of prototype measurements to their appointment. The audiology appointment will include routine ear and hearing measures, such as otoscopy (visual ear exam) and pure tone

Title: "Pilot Validation of a Prototype Mobile Health Tympanometer"
PI: [name], MPH
Institution: University of Arkansas for Medical Sciences

testing. The prototype device will be conducted before the commercial tympanometry. Audiologists will be asked to complete the prototype measurement and interpretation prior to the commercial device to limit bias in study results. We anticipate approximately 3 audiologists from UAMS and 2 audiologists from AC being involved in the study. Audiologists will be provided initial training and a demonstration of the prototype device and given instruction on how to troubleshoot and who to contact should an unanticipated problem occur. The tympanometric measurement takes roughly 10-15 seconds per ear to collect. We anticipate the prototype measurement and data entry will take no more than 5 minutes to complete during the audiological appointment.

The resulting tympanograms from the prototype device and the clinical tympanometer will be interpreted by the audiologist and entered in a secure Research Electronic Data Capture (REDCap) database. The audiologist will also answer a few brief questions during/after testing each participant in a REDCap form on device performance for both the prototype and commercial tympanometers.

Specifically, the order of events will be as follows:

1. Audiologist will test each ear of the participant with the prototype device and interpret the tympanogram. These findings will be entered in a secure Research Electronic Data Capture (REDCap) database in real time using a tablet or computer.
2. Next, the audiologist will test each ear of the participant with a commercial tympanometer, interpret the results and enter them in the database as described above.
3. The audiologist will complete 4 questions on each device performance between testing with each device (steps 1 and 2) if time permits, or after completion of testing with both the devices, and document it in a secure REDCap database.

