Testing machine learning algorithm: The performance of the machine learning algorithm will be tested by using raw data from the prototype mHealth tympanometer obtained from the pilot validation study. The ML will interpret the raw tympanometric data and classify the results into Type A, B, and C. The classification by the ML algorithm will be compared to audiologists' interpretation, and concordance will be assessed. The audiologists interpreting the data will be blind to the ML algorithm and the ML algorithm will not be provided the audiologist interpretation.

Study Population

The study population consists of patient participants presenting to the UAMS and AC Audiology Clinics for audiological evaluation. The goal is to enroll enough participants to have a total of 60 ears (40 adult ears and 20 pediatric ears) with data from both the prototype and commercial tympanometers. If test results cannot be obtained, which can happen in some ears with tympanometry, then we will enroll additional participants until we reach 40 adult ears with data from both devices and 20 pediatric ears with data from both devices. This may involve inviting up to 20 adults and 20 children to participate in the study.

Title: "Pilot Validation of a Prototype Mobile Health Tympanometer"
PI: [name], MPH
Institution: University of Arkansas for Medical Sciences

Inclusion Criteria

- Individuals, 1-year old and older
- Presenting to the UAMS or AC Audiology Clinics for evaluation where tympanometry is warranted for testing at the discretion of the audiologist
- Presence of various middle ear health states/pathologies that result in Type A, B, C tympanograms; examples include normal, occluding cerumen, effusion, perforation, retraction otosclerosis, cholesteatoma, ossicular chain discontinuity, myringitis, and tympanosclerosis
- English-speaking

Exclusion Criteria

- Children or adults with cognitive disabilities
- Unable to provide consent/assent
- Individuals who are unable to sit still
- Any other condition, that, in the opinion of the investigator, might interfere with the safe conduct of the study or place the participant at increased risk

Recruitment

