**Hypothesis 1:**

The diagnostic accuracy (sensitivity and specificity) of the prototype device based on audiologist's interpretation as compared to the commercial tympanometer based on audiologist's interpretation is 80% or greater.

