### 4 Outcomes, Exposures, and Additional Variables of Interest

#### 4.1 *Outcome(s)*

Table 2. Description of outcome variables

Outcome	Description	Variables and Source	Specifications
Primary Outcome(s)			
Categorical classification of tympanogram types A, B, C  1) Audiologist's interpretation of commercial device versus audiologist's interpretation of prototype device  2A) Audiologist's interpretation of prototype device versus machine learning algorithm's interpretation of prototype device  2B) Audiologist's interpretation of commercial device versus machine learning algorithm's interpretation of prototype device	Tympanograms can be classified into types (Type A, B, C) that help to determine if an eardrum has fluid behind it, is retracted, or perhaps has a perforation, all common ear disease states. Type A indicates normal ear function, and types B and C indicate abnormal middle ear function.	Audiologist commercial device classification (left, right): Tymp_type_au_com_l; Tymp_type_au_com_r  Audiologist prototype device classification (left, right): Tymp_type_au_proto_l; Tymp_type_au_proto_r  Machine learning algorithm prototype device classification (left, right): Tymp_type_ml_proto_l; Tymp_type_ml_proto_r  Forms: 1) Data collection form: Audiologist interpretation and performance for mHealth tympanometer  2) Data collection form: Audiologist interpretation and performance for commercial tympanometer  3) ML Algorithm Interpretation form	1=A; 2=B; 3=C; 4=CNE (could not evaluate)
Secondary Outcome(s)			
Ear canal volume, static admittance and	Numerical measures	Commercial device (left, right):	Numerical measures

tympanometric peak pressure	Commercial device versus prototype device	
ecv_com_l; sa_com_l; tpp_com_l; ecv_com_r; sa_com_r; tpp_com_r
 
Prototype device (left, right): ecv_proto_l; sa_proto_l; tpp_proto_l; ecv_proto_r; sa_proto_r; tpp_proto_r
 
Forms: 1) Data collection form: Audiologist Interpretation and Performance for commercial tympanometer  2) ML Algorithm Interpretation form

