### 5.3 Analysis of Primary Endpoints

The primary outcome is the classification of the tympanogram types, which can be categorized into one of the three categories A, B, and C. The classification of tympanogram types from the commercial device (based on audiologist's interpretation) will be considered as reference standard (gold standard). In the subsequent section, the unit of cluster will refer to subjects who contribute to tympanogram types for left and right ears using the prototype as well as the commercial device. The analysis will be done based on a 2-level outcome, namely A (normal) vs B/C (diseased).

Diagnostic accuracy of the prototype device based on audiologist's interpretation: The diagnostic accuracy of the prototype device (based on audiologist's interpretation) will be estimated using sensitivity and specificity. The sensitivity and specificity will be estimated using a binary outcome – A (normal) vs B/C (diseased). To ensure the maximum use of the available data, the estimates of sensitivity and specificity will

be computed at ear-level. Taking into consideration the potential correlation between the two ears, the sensitivity and specificity will be estimated using generalized estimating equation (GEE), with a robust (sandwich) variance estimator and unstructured correlation matrix.

**Secondary analysis of primary endpoints:** The secondary analysis of primary endpoints will constitute additional measures of diagnostic accuracy namely – positive predictive value (PPV), negative predictive value (NPV), positive likelihood ratio (PLR), and negative likelihood ratio (NLR). To obtain estimates of PPV and NPV, the disease prevalence will be set at 0.20 (estimate of disease prevalence may be updated).

**Analysis based on 3-level outcome:** The performance of the prototype device will be presented using a three-by-three confusion matrix. The overall accuracy will be computed from the confusion matrix. We will also compute separate estimates of sensitivity and specificity separately for tympanometric tracing types B and C respectively.

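### The commercial reading that serves as gold standard is not masked to the prototype reading of the same ear, so accuracy is likely biased upward by an unknown amount

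*Protocol*

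**What the plan says.** The Protocol (Study Design and Procedures) sets out the visit in steps, and SAP 2.1 repeats them. First, "Audiologist will test each ear of the participant with the prototype device and interpret the tympanogram", with entry in REDCap in real time. Then: "Next, the audiologist will test each ear of the participant with a commercial tympanometer, interpret the results and enter them in the database". The reason given for the order is: "Audiologists will be asked to complete the prototype measurement and interpretation prior to the commercial device to limit bias in study results".

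SAP 5.3 says that the commercial classification, as read by the audiologist, "will be considered as reference standard (gold standard") for sensitivity and specificity. Hypothesis 1 (SAP 1.3) is that the prototype's accuracy "as compared to the commercial tympanometer based on audiologist's interpretation is 80% or greater". Hypothesis 2B uses the same reference for the machine learning (ML) reading.

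On readers, the Protocol says: "We anticipate approximately 3 audiologists from UAMS and 2 audiologists from AC being involved in the study". It does not divide them between devices. The only masking described is between audiologist and algorithm: "The audiologists interpreting the data will be blind to the ML algorithm and the ML algorithm will not be provided the audiologist interpretation". No second reader, masked re-reading or adjudication of the commercial tracing is planned. SAP 5.8 (Sensitivity analysis) is marked not applicable, and SAP 6 (Limitations) deals only with missing data.

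SAP Table 2 lists the commercial numerical measures for each ear: "ecv_com_l; sa_com_l; tpp_com_l; ecv_com_r; sa_com_r; tpp_com_r".

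**The concern.** The sponsor saw the risk of reader bias and dealt with half of it. The prototype reading is protected, but the reference is made by a reader who already has an answer in mind for that ear. Type A, B or C is a judgement on a graphical display, so a borderline commercial tracing can be drawn toward the class just entered. Each time that happens, a disagreement between the devices becomes an agreement, and both sensitivity and specificity rise.

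Objective 1 rests on exactly this pair of readings, as do the device kappa and Bowker analyses in the Protocol's Data Analysis section. The estimates are meant to guide design changes and to support the application for a larger validation study. A shift in the estimate would carry forward into both.

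**Working it through.** **Figures in the plan.** The point disputes none of them, and masking would change none.
- SAP 2.2 gives 95% half-widths of 0.25-0.33 for sensitivity and 0.12-0.18 for specificity, each at 0.80. Clopper-Pearson intervals with 12 or 6 diseased units and 48 or 24 normal units (intra-class correlation 0 or 1) give 0.244-0.331 and 0.121-0.173, within 0.01 of the stated values.
- The Protocol's power of 0.89 for kappa 0 versus 0.3 in 60 ears comes out at 0.895 with equal A/B/C shares (assumed) and independent ears.

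**Inputs for the illustration.**
- 60 ears (both documents) and prevalence π = 0.20 (SAP 2.2). Prevalence 0.50 is added as an assumption, because the Protocol says patients with pathology will be selected.
- True sensitivity and specificity (Se, Sp): assumed, just below or at the 80% level.
- Pull q, the share of reference readings that would have disagreed with the prototype but are changed to match it: assumed. The documents give no value. A masked reference has q = 0.

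**Formulas.** A pulled false positive becomes a true positive, and a pulled false negative becomes a true negative:

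Se_obs = [πSe + q(1−π)(1−Sp)] / [πSe + q(1−π)(1−Sp) + (1−q)π(1−Se)]

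Sp_obs = [(1−π)Sp + qπ(1−Se)] / [(1−π)Sp + qπ(1−Se) + (1−q)(1−π)(1−Sp)]

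**Worked case.** With π = 0.20 and true 0.75/0.80, the expected counts in 60 ears are TP 9, FN 3, FP 9.6, TN 38.4. At q = 0.25, 2.4 FP become TP and 0.75 FN become TN, about 3 ears in all. Se_obs = 11.4/(11.4 + 2.25) = 0.835. Sp_obs = 39.15/(39.15 + 7.2) = 0.845.

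| Prevalence | True Se/Sp | q | Apparent Se | Apparent Sp |
|---|---|---|---|---|
| 0.20 | 0.75/0.80 | 0.10 | 9.96/12.66 = 0.79 | 38.70/47.34 = 0.82 |
| 0.20 | 0.75/0.80 | 0.25 | 11.40/13.65 = 0.835 | 39.15/46.35 = 0.845 |
| 0.20 | 0.70/0.75 | 0.25 | 11.40/14.10 = 0.81 | 36.90/45.90 = 0.80 |
| 0.50 | 0.70/0.75 | 0.25 | 22.875/29.625 = 0.77 | 24.75/30.375 = 0.81 |

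The third and fourth rows differ only in prevalence. Both measures reach 0.80 at prevalence 0.20, but sensitivity does not at 0.50.

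**Objective 2B.** Suppose the algorithm matches the audiologist's prototype reading in a share m of ears, independently of the reference given that reading. Then the ML value is m × (audiologist value) + (1−m) × (1 − audiologist value), so the ML lift is (2m−1) times the audiologist's. Take π = 0.20, true audiologist values 0.70/0.70, q = 0.25 and m = 0.90 (assumed). The audiologist's values move from 0.70/0.70 to 0.816/0.762, and the ML values from 0.66/0.66 to 0.753/0.709. The lifts are about 12 and 6 points for the audiologist, and 9 and 5 for the algorithm.

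**Objective 2A.** Both readings are of the prototype and each is masked to the other. The commercial reading does not enter.

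**The case against.** **Direction and size are not established.** This stands. The documents show an opportunity for carry-over, not its occurrence. A reader who deliberately contrasts the two tracings could move the result the other way. With true 0.80/0.80 at prevalence 0.20, flipping 5% of concordant reference readings away from the prototype gives 9.12/13.44 = 0.68 and 36.48/46.56 = 0.78. The commercial reading is also part of the patient's scheduled care, which is a reason to judge it on its own merits. Upward remains the more plausible direction.

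**The illustration is a chosen scenario.** This stands too. It applies the pull to every discordant ear, although clear-cut disagreements should be harder to shift, and it depends on prevalence. It shows what is possible and does not estimate the bias.

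**The documents never say that one and the same audiologist reads both devices.** That is correct, but the steps speak of the audiologist throughout a single visit, that person also rates both devices, and no other reader is provided for.

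**It is a pilot with wide intervals.** The objectives are preliminary estimates, SAP 5.3 has no pass/fail rule at 80%, and the planned sensitivity half-width of 0.25-0.33 exceeds the illustrated shifts. This lowers the stakes. It does not remove the point, because an interval describes random error and does not allow for a shifted reference.

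**Stronger readings that a reader might infer.** One is that the accuracy estimates are inflated and a device below 80% will be passed. The documents support neither a known inflation nor a decision at 80%. Another is that the audiologist-versus-ML comparison of the prototype is distorted. That comparison is Objective 2A, which is unaffected. Comparing Objective 1 accuracy with Objective 2B accuracy is not a planned analysis, and in the example above 2B shares most of the lift.

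**Conclusion.** The point holds as a likely upward bias of unknown size in sensitivity and specificity for Objective 1, with a smaller effect on Objective 2B and none on Objective 2A. The fixed order masks the index reading and leaves the reference open, and nothing in SAP 5.8 or SAP 6 deals with that.

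Under the assumed pulls, at prevalence 0.20, the shift is about 4 and 2 points (sensitivity, specificity) at 10% and 8.5 and 4.5 points at 25% when the truth is 0.75/0.80. These figures rest on the pull fraction, the true accuracy and the prevalence. The first two are not in the documents, and the third is only an SAP assumption. The change is worth making because it is cheap. The study does not fail without it.

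**What to change.** 1. In SAP 5.8, add a sensitivity analysis that derives the commercial A/B/C class by rule from the recorded commercial ear canal volume, static admittance and tympanometric peak pressure. Recompute sensitivity and specificity for Objectives 1 and 2B against it.
2. Have the study team fix the numeric cut-offs before enrolment. If enrolment has started, they should be set by someone who has not seen the study tracings. Cut-offs agreed just before data lock by audiologists who have already read both tracings would bring the unmasked reader back in.
3. State in the rule how tracings with no measurable peak are classed. The documents do not say how peak pressure is recorded for them.
4. Optionally, apply the same rule to the recorded prototype values, so that differences between rule and expert reading are not mistaken for carry-over.
5. In SAP 6, state that the reference reading is not masked to the prototype reading and that the likely direction of the bias is upward.

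The cost is SAP text, agreement on cut-offs and one more analysis run, with no extra reader, visit or measurement. A rule-based class may differ from expert reading in atypical tracings, and about 12 diseased ears (60 × 0.20) give low precision. The analysis is therefore supportive and leaves the primary reference unchanged.

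Two other measures would not help. Reversing the order would only unmask the prototype reading instead. Locking the prototype entry before the commercial form opens would protect that entry, not the reference. A second audiologist reading the commercial tracings without the prototype result would be more direct, but needs staff time and saved commercial tracings, and the documents do not say whether these are kept.
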